### **Intervention**

Patients will be randomly assigned to 60 days of oral Zinc Gluconate capsules (one capsule of 200mg daily) versus the placebo capsules. The participants will be given a container filled with 60 capsules. They will be instructed to take 1 capsule once a day 20 minutes before the morning meal in their residence. The starch placebos will be identical to zinc supplements in size, color, and shape hence both patients and investigators will be unable to tell whether participant will be on zinc supplementation or placebo.

All participants will receive the same adapalene 0.3% + benzoyl peroxide 2.5% preparation to be applied two times a day on affected areas. Patient education on Acne Vulgaris, Zinc sources, and basic skin care will be performed on all patients. Instructions will be given to avoid intake of other medication or supplementation during the 60-day trial.

### **Checking of Compliance**

Participants will be given a Daily Monitoring Sheet where they can note if they have taken

the capsule for the day, as well as side effects or other remarks. The number of remaining capsules will be checked every 2 weeks during follow-up. Patient will be required to bring medicine bottle on follow-up for the pill count.

### **Final evaluation**

After 60 days of either placebo or zinc gluconate, the participant will be instructed to follow up for re-assessment. The GAGS and acne inflammatory score will be re-evaluated. The investigator will perform an examiner's assessment score and the patient will also give a self-assessment score.

### **Outcome measures**

The primary outcome measure will be the change in inflammatory scores, GAGS scores of the zinc and placebo groups from initial consult to the end of the trial. The secondary outcome measures include the examiner's assessment score and the patient's self-assessment score.

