compared to oxytetracycline in a study by Michaelsson et al, and showed no significant difference in the effect on acne vulgaris. On the other hand, a study by Dreno et al showed that minocycline was superior to oral zinc in the treatment of acne vulgaris and a study by Cunliffe et al showed that although oral zinc was correlated with decreased inflammatory lesions, tetracycline has a superior effect. These studies compared oral zinc with antibiotics, which are already established treatment options for acne vulgaris. There are some instances, however, when patients are already resistant to antibiotics or are reluctant to take antibiotics for long-term. Oral zinc for acne vulgaris may be useful for patients who cannot or do not want to take oral antibiotics in the long-term and for those who already have erythromycin- or clindamycin-resistant strains of *Cutibacterium acnes* (*Propionibacterium acnes*). Multiple sources showed that when oral zinc was compared to placebo, there was a significant improvement in inflammation and number of acne lesions. Furthermore, adding zinc salts in vitro to culture media of *Cutibacterium acnes* (*Propionibacterium acnes*) reduced resistance of the bacteria to erythromycin. One of the anti-inflammatory effects of oral zinc in acne was found to be in the inhibition of TLR2 surface expression by keratinocytes. Studies about giving oral zinc gluconate supplements versus placebo in the Philippine setting have not yet been done.

The inflammatory score is a grading system that measures inflammatory lesions only. It includes locations such as the face, chest and back. For each location, papules, pustules and nodules are counted. A factor based on the lesion (papule=3, pustule=4, nodule=5) is used to be multiplied to a grade equivalent to the number of lesions. The subtotal scores are added with a maximum possible total score of 144.

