The Global Acne Grading System (GAGS) is an acne severity scale that includes six locations on the face, chest, and back. A factor based on surface area and distribution of pilosebaceous units is provided for each of the six locations, and grades are based on the type of lesions per area (1 for  $\geq$  one comedone, 2 for  $\geq$  one papule, 3 for  $\geq$  one pustule, and 4 for  $\geq$  one nodule). The factor and the grade are multiplied to get a local score. The local scores are then added with a maximum possible global score of 44. Acne severity is rated as mild, moderate, severe, and very severe with corresponding cut-off scores.

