### **Research Question**

Does oral zinc gluconate supplementation improve inflammatory acne as measured by the inflammatory score and GAGS score in diagnosed acne vulgaris patients?

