#### **SPECIFIC**

- To determine the demographic and clinical profile of Acne Vulgaris patients
- To determine the disease activity measured by the inflammatory score and GAGS score of acne vulgaris patients on initial consult, at 4 weeks, and at 8 weeks.
- To determine if there is a significant difference in disease activity as measured by the inflammatory score and GAGS score among acne vulgaris patients given placebo and oral zinc gluconate.

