### Improvement in the disease activity

This will be assessed by determining the difference in the GAGS and inflammatory scores of a patient at the start and at the end of the clinical trial. The GAGS and inflammatory scores will be measured by the same investigators at the start and at the end of the trial. Secondary measures include the examiner's assessment and patient's self-assessment scores at the end of the trial.

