### Statistical analysis plan

For the profiling of patients, quantitative variables (e.g. age, inflammatory scores, and GAGS scores) will be summarized using the mean and standard deviation or median and range (Min-max) if the data appears scattered. Meanwhile, qualitative variables (e.g. sex, examiner's assessment, patient's self-assessment) will be described as frequencies and percentages. The point and 95% confidence interval estimate of the mean inflammatory scores and GAGS scores

of the two treatment groups will be measured at baseline, at one month, and at the end of the trial. Lastly, independent two-sample t-test will be used to compare the two treatment groups in terms of: 1) the mean change in the inflammatory scores from baseline to end of the trial; 2) the mean change in the GAGS scores from baseline to end of the trial. Alternatively, Mann-Whitney U-Test will be used as an alternative if the data will be dispersed. Repeated measures ANOVA will be used to compare the inflammatory score and GAGS score of acne vulgaris patients on initial consult, at 4 weeks, and at 8 weeks. Friedman test will be used as a non-parametric alternative.

A 5% level of significance will be used in this hypothesis testing. SPSS version 25.0 will be used for all output and the necessary descriptive and inferential statistics in this study.

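### Two scores are both primary and each is tested at 5%, with no order, adjustment or success rule; if either score suffices, the two-sided false-positive rate from these two tests is 6.5% to 9.75% (assumed correlation 0.95 to 0)

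*Combined protocol and SAP*

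**What the plan says.** Outcome measures gives a single primary outcome that contains two scores: "The primary outcome measure will be the change in inflammatory scores, GAGS scores of the zinc and placebo groups", measured from first consult to the end of the trial. The two are not ranked.

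The Statistical analysis plan states that an "independent two-sample t-test will be used to compare the two treatment groups in terms of" two numbered quantities, the mean change in inflammatory score and the mean change in GAGS. A Mann-Whitney test is the fallback for each. On the error rate it says only: "A 5% level of significance will be used in this hypothesis testing". Dummy Table 5 has one p-value column and a row for each score.

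Three other sections pair the scores. The Research Question asks about improvement "as measured by the inflammatory score and GAGS score in diagnosed acne vulgaris patients". The third specific objective is "To determine if there is a significant difference in disease activity as measured by the inflammatory score and GAGS score among acne vulgaris patients". The definition of improvement reads "This will be assessed by determining the difference in the GAGS and inflammatory scores of a patient". None of them says what result counts as success.

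Sample Size Computation takes its effect size from the inflammatory score of an earlier zinc gluconate trial. GAGS has no planning assumption.

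**The concern.** With two primary tests, the error rate and power of the overall conclusion depend on how the tests are combined, and the plan does not say how.

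- If zinc is declared effective when either score reaches 5%, the chance of a false declaration is above 5%.
- If both must reach 5%, the false-positive rate cannot exceed 5%, but a real effect is more easily missed.
- If one score is significant and the other is not, nothing says what to conclude. The choice could then be made after the results are seen.

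A split result is possible because the scores are built differently. The Review of Related Literature says of the first: "The inflammatory score is a grading system that measures inflammatory lesions only". It weights papules, pustules and nodules by a grade for their number. For GAGS, "grades are based on the type of lesions per area": one lesion of a type is enough for the grade, and comedones count. A fall in lesion numbers can therefore lower the inflammatory score while GAGS stays the same.

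**Working it through.** **Inputs from the documents.** Two primary between-arm tests and a 5% level (Outcome measures; Statistical analysis plan). Effect size 0.6708327, 12 patients (6 per group) for 80% power, and 20% added for dropout (Sample Size Computation). 32 numbered bottles (Treatment allocation and blinding).

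**Assumptions.** The documents give neither the correlation r between the two changes nor the sidedness. I take r = 0, 0.5, 0.8 and 0.95, two-sided tests and equal arms.

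**Step 1: the plan's own figure.** For the between-arm factor of a repeated measures ANOVA with m = 3 visits and within-patient correlation ρ, the noncentrality is f²·N·m / (1 + (m − 1)ρ). The plan does not state ρ. With ρ = 0.3 and N = 12 this is 0.450 × 12 × 3 / 1.6 = 10.1, and power is 81.8%. The same ρ gives 12, 16, 18 and 24 patients for 80%, 90%, 95% and 99% power, which matches all of Table I. So 0.67 behaves as Cohen's f, and the sizing used the between factor of that model.

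**Step 2: no effect on either score.** At r = 0, the chance of at least one significant result is 1 − 0.95² = 0.0975. For r above 0 it is the bivariate normal probability that |Z1| or |Z2| exceeds 1.96. Call it p. Each test has level 0.05, so P(both) = 0.10 − p and P(exactly one) = 2p − 0.10.

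| r | At least one | Both | Exactly one |
|---|---|---|---|
| 0 | 9.75% | 0.25% | 9.5% |
| 0.5 | 9.1% | 0.9% | 8.1% |
| 0.8 | 7.8% | 2.2% | 5.6% |
| 0.95 | 6.5% | 3.5% | 2.9% |

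Simulated t-tests at 6 and 16 per arm agree: about 9.8% at r = 0, and 6.5% to 6.6% at r = 0.95. Counting only false results that favour zinc, the rate is at most 4.9% for non-negative r, against 2.5% for one test.

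**Step 3: power if both scores must be significant.** I assume the same effect on both scores. For two arms d = 2f = 2 × 0.6708 = 1.34. That is the change-score effect only if ρ = 0.5. If 0.67 describes the month-2 difference in raw-score SD units with equal baselines, the change has SD √(2(1 − ρ)) times the raw SD. At ρ = 0.3, d = 1.34 / √1.4 = 1.13. For dropout, 32 × 0.8 = 25.6, or about 13 per arm.

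| d | Per arm | Single test | Both required (r = 0 to 0.95) |
|---|---|---|---|
| 1.34 | 16 | 95.6% | 91.5% to 94.5% |
| 1.34 | 13 | 90.7% | 82.2% to 88.5% |
| 1.13 | 16 | 87.4% | 76.3% to 84.6% |
| 1.13 | 13 | 79.2% | 62.7% to 75.4% |
| 0.67 (0.67 read as d) | 16 | 45.1% | 20.3% to 40.1% |

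Single-test power is from the noncentral t distribution. Joint power at r = 0 is its square (for example 0.956² ≈ 0.915, using the unrounded 0.9564). Joint power at the other values is simulated.

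**The case against.** The strongest defence is that the plan means both scores. The Research Question and the third objective join them with a conjunction, and under a both-required rule there is no inflation. That reading is possible. But those sentences say what is measured, not what result is needed, and Outcome measures joins the two scores only with a comma. It therefore cannot be said that the trial will run at nearly 10% error; a reader might infer this, but the plan adopts no either-score rule.

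A second defence is that the inflammatory score leads because the trial was sized on it. The sizing gives a good reason to put it first, but Outcome measures still lists GAGS as primary.

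Third, 9.75% is an upper bound. Both scores grade papules, pustules and nodules on the face, chest and back of the same patients, and the same investigators assess them. A correlation near 0 is hard to credit. This stands.

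Fourth, Table 5 prints both p-values, so a split result would be visible. This also stands. It would be too strong to say that the plan leaves its research question unanswered; what is missing is a decision rule.

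Finally, one might treat the repeated measures ANOVA as a mere description of change over time. The documents do not settle that: the sample size rests on its between-arm factor, while the analysis section gives the between-arm comparison to the t-test. If the ANOVA is also used to compare arms, the figures above do not count it.

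**Conclusion.** The point holds in conditional form. Two unranked primary scores are each tested at 5%, and no rule joins them. If either suffices, the two-sided false-positive rate from the two change-score tests is 6.5% to 9.75%, with the upper end unlikely. If both are required, the rate is at most 5% and the cost is power. The range rests on assumed correlations and on two-sided tests.

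This should be corrected, since two unadjusted primary tests exceed the stated 5% under one natural reading. It does not show that the sponsor intends that reading.

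**What to change.** Before the code is broken, state one rule in both Outcome measures and the Statistical analysis plan:

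- The between-arm change in inflammatory score from baseline to month 2 is the primary test at two-sided 5%. It is the only score with a planning basis.
- GAGS is tested at two-sided 5% only if the first test is significant.
- Both scores are reported as in Table 5 whatever the result.

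Also state the role of the repeated measures ANOVA or Friedman analysis. For each score, name one between-arm test as confirmatory and the other as supportive.

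Study Design dates the trial from December 2018 to July 2019. If the code has already been broken, disclose the rule as post hoc.

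The change is a few sentences and needs no extra patients. The inflammatory-score test keeps its full 5% level; in exchange, GAGS alone cannot support a positive conclusion.

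Requiring both scores would also control the error and would fit the paired wording of the objectives. Its power loss is not reliably small, however. It runs from 1 to 4 percentage points at 16 per arm with d = 1.34 to between 4 and 17 points at 13 per arm with d = 1.13, and it is larger still if 0.67 is d.

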### **Stopping Guidelines**

[figure not shown]
Criteria for stopping the intervention include anaphylactic reaction or allergies to the medications, and severe gastrointestinal symptoms. Patients with severe adverse reactions will be treated accordingly to relieve symptoms. They will be considered as "withdrawals" of the study, and still receive proper treatment for acne vulgaris.

### **Dropouts and Withdrawals**

Withdrawals are defined as patients who discontinued the study for known reasons (did not comply with instructions, had severe adverse reactions). Dropouts are defined as patients who cannot be contacted, had no more follow up, and whose outcomes are unknown by the end of the study period.

### **Study Framework**

Figure 1. Study Framework

### Sample Size Computation

The sample size is computed using G\*Power software. The effect size used was based on “Low Doses of Zinc Gluconate for Inflammatory Acne” by Dreno, P et al. (1989). According to this, the inflammatory score was statistically lower in the Zinc group than in the Placebo group at 2nd month of observation with p-value less than 0.02. The computed effect size was 0.6708327, this was used given that there was no effect size convention available in G\*Power for repeated measures between factors (ANOVA, F-test). The computed sample size of 12 (6 per group) was estimated using 0.05  $\alpha$ -level of significance at 80% actual power of analysis. Twenty percent of the computed sample size was added to adjust for the dropout rate. Thus, the minimum required sample size is 15. The sample sizes for power of analysis are shown in Table I.

Power of Analysis	Sample Size	Group 1	Group 2
99%	24	12	12
95%	18	9	9
90%	16	8	8
80%	12	6	6

Table I. Sample sizes for power of analysis

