### **Treatment allocation and blinding**

The Solgar Zinc Gluconate 50mg will be repackaged by the TARC Pharmacy Laboratory of the University of Santo Tomas into the clear size 0 capsules. The same laboratory will prepare the placebo capsules and package the cornstarch placebo into the same clear size 0 capsules. This repackaging is necessary to ensure that the physicians and the participants will be blinded during the study. The capsules will be packaged in uniform airtight containers with 60 capsules per container. A third person not directly involved in care and assessment of the subjects, who also did the randomization, will be tasked to encode the capsules into groups A and B. Bottles will be labelled with the corresponding patient number only. Both the physician in charge and the patients will be unaware of which capsules contain Zinc Gluconate or placebo. During the study, patients will be asked to draw a number from 1 to 32, and he/she will get the corresponding bottle. The code will then be revealed during the data analysis portion to allow the statistician to segregate the results into the proper groups.

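### The 80% power claimed for 12 patients belongs to a repeated-measures F test; the primary t-test on change has about 43–56% power with 6 per arm

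*Combined protocol and SAP*

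**What the plan says.** The Sample Size Computation section takes its effect from a published zinc–placebo comparison of inflammatory scores at month 2: "The computed effect size was 0.6708327". It says this value was used because G*Power has no effect size convention "for repeated measures between factors (ANOVA, F-test". It then reports that "The computed sample size of 12 (6 per group) was estimated using 0.05" "level of significance at 80% actual power of analysis". Table I lists totals of 12, 16, 18 and 24 for 80%, 90%, 95% and 99% power. After a 20% allowance for dropout: "Thus, the minimum required sample size is 15".

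The Outcome measures section makes the change in inflammatory and GAGS scores from initial consult to end of trial primary. For that outcome, the Statistical analysis plan says an "independent two-sample t-test will be used to compare the two treatment groups in terms of: 1) the mean change in the inflammatory scores", and likewise in GAGS, with Mann-Whitney as the alternative. Dummy Table 5, the only dummy table with a p-value column, reports this comparison. Repeated-measures ANOVA also appears in the plan, but only to compare scores across the three visits.

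The Treatment allocation and blinding section implies a different size: "patients will be asked to draw a number from 1 to 32".

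**The concern.** The test that was powered is not the test that answers the primary question. A between-factors main effect compares arm means averaged over all visits. Powering it at the full effect credits the trial with a full zinc–placebo difference at baseline, where randomisation makes the expected difference zero. It also gains precision from averaging several measurements, which a change score does not.

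A trial that stopped at the stated minimum of 15 (12 completers) would be reported as having 80% power, when its primary test has about an even chance of detecting the assumed effect. A null result could then be misread as evidence against zinc from an adequately powered trial.

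**Working it through.** **Inputs from the protocol.** Effect size 0.6708327; alpha 0.05; 6 per group; 20% dropout; scores at baseline, 4 and 8 weeks (m = 3); 32 bottles.

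**Assumptions, because the text is silent.** 0.6708 is Cohen's f, as an F test requires, so d = 2f = 1.342 for two equal groups. Testing is two-sided; the plan says only "A 5% level of significance will be used in this hypothesis testing". The SD is the same at each visit, with a common between-visit correlation ρ.

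**Step 1: reproduce Table I.** For the between-factors F test, λ = f²·N·m / (1 + (m − 1)ρ), with 1 and N − 2 degrees of freedom. At N = 12, m = 3 and ρ = 0.30, λ = 0.4500 × 36 / 1.6 = 10.13, and power is 81.8%.

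| N | Power, ρ = 0.30 | Smallest even N for | Result | Table I |
|---|---|---|---|---|
| 12 | 81.8% | 80% | 12 | 12 |
| 16 | 92.7% | 90% | 16 | 16 |
| 18 | 95.5% | 95% | 18 | 18 |
| 24 | 99.0% | 99% | 24 | 24 |

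All four rows match for ρ from about 0.26 to 0.30. At ρ = 0.5 the sizes would be 14, 18, 22 and 30, and N = 12 would give 72.8%. The dropout step is sound: 12 × 1.2 = 14.4, rounded up to 15, and 12 / 0.8 = 15.

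**Step 2: power of the primary t-test.** SD of change = SD·√(2(1 − ρ)), so d_change = 1.342 / √(2(1 − ρ)). This is 1.342 / √1.4 = 1.134 at ρ = 0.30 and 1.342 / √1 = 1.342 at ρ = 0.5. Power is from the noncentral t with 2n − 2 degrees of freedom and noncentrality d_change·√(n/2). At n = 6 the noncentrality is 1.964 and 2.324 respectively.

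| Per arm | Table I | t-test, ρ = 0.30 | t-test, ρ = 0.5 |
|---|---|---|---|
| 6 | 80% | 43% | 56% |
| 8 | 90% | 56% | 70% |
| 9 | 95% | 62% | 76% |
| 12 | 99% | 76% | 88% |
| 13 | – | 79% | 91% |
| 16 | – | 87% | 96% |

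Reaching 80% takes 14 per arm (ρ = 0.30) or 10 per arm (ρ = 0.5). If all 15 patients complete (7 + 8), power is 53% to 67%.

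**Step 3: sensitivity.**
- The t-test reaches 80% at 6 per arm only when ρ is about 0.72 or more. With three visits, the F test needs N = 18 at ρ = 0.7, so no single ρ supports both figures.
- One-sided testing with d_change = 1.342 gives 70% at 6 per arm.
- Table I can also be matched with 2, 4 or 5 measurements (ρ about 0.01–0.07, 0.34–0.38 and 0.38–0.415). Across all matching settings from 2 to 5 measurements, the t-test has 32–49% power at 6 per arm.
- If the arm difference is zero at baseline, half at month 1 and full at month 2, its average is half the full effect. The F test itself then has 30% power at N = 12 (ρ = 0.30).
- If 0.6708 is really Cohen's d, the t-test has 14–18% power at 6 per arm and 34–45% at 16 per arm (ρ = 0.30 to 0.5).

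**The case against.** The strongest reply is that 15 is only a floor. With 32 bottles prepared, the trial may well enrol 32. At d = 1.34, 16 per arm gives 87–96% and 13 per arm gives 79–91%, so the trial need not be underpowered. This stands as a limit on the practical harm. It does not rescue the text: the sample size section never mentions 32, calls 15 the required minimum and attaches 80% power to 12.

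A second reply is that ρ and the number of measurements are not stated, and that the upper figure of 56% uses a ρ that does not reproduce Table I. That is correct. It makes 56% generous, since every matching setting examined gives less than 50%.

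A third is that reading 0.6708 as d is unlikely, because f reproduces the table. Reproduction shows that the number was entered as f. It does not show that it was calculated as f, because the derivation is not given. Nor does the text show whether the value was meant as a month-2 or a visit-averaged effect. The figures under d are a reason to state the definition, not the main result.

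Finally, Table I contains no slip of arithmetic. The fault is that it is attached to the wrong test.

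**Conclusion.** The concern holds. At the stated size of 6 per arm, the primary analysis does not have the claimed 80% power. It has about 43% (ρ = 0.30) to 56% (ρ = 0.5), assuming 0.6708 is Cohen's f, the month-2 effect applies in full to the change, and testing is two-sided. The mismatch between the powered test and the primary test is plain from the text and certain; the exact percentages depend on those assumptions. The statement needs correcting before the trial relies on it. The practical consequence is serious if enrolment stops near 15 and much smaller if all 32 are enrolled.

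**What to change.** Rewrite the sample size paragraph and replace Table I:

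- State 32 randomised (16 per arm) as the planned size. After 20% dropout, 32 × 0.8 = 25.6, or about 13 per arm.
- State whether 0.6708 is f or d, how it was derived, the assumed between-visit correlation, and whether the test is one- or two-sided.
- Give power for the t-test on change. With d = 1.34 and two-sided 5% testing, it is 87% at 16 per arm and 79% at 13 per arm for ρ = 0.30, and 96% and 91% for ρ = 0.5.
- Give the difference in mean change detectable with 80% power: 1.02 SD of the change at 16 per arm and 1.15 SD at 13 per arm.
- Delete the statement that 12 or 15 patients provide 80% power.

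The cost is one paragraph and one table. Power at any given number will look less favourable than in Table I, but no patients are needed beyond the 32 for whom bottles are numbered.
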